1. RATIONALE AND AIM OF THE STUDY

People lose collagen all over the body, not just in the face; skin roughness and laxity of the dorsum of the hands can result from chrono and photo-aging.

This skin roughness and laxity can range from very mild to severe; injection procedures can provide new tone and firmness to the skin of the hand dorsum.

Dermal fillers are the most used non-permanent injectable materials available today to correct skin flaccidity and roughness on the dorsum of the hands. They give immediate aesthetic effect due to elastic gel matrix injected and impart longer term effects due to bio stimulation, promoting new collagen formation.

The objective of this study is to investigate the aesthetic performance of the Hyaluronic acid (HA)-based dermal filler Prohilo® Body injected by a blunt tip microcannula (25G or 22G, preferably 22G), with fanning technique through a single entry point performing 5 passages and injecting 0,3 ml per passage, 1,5 ml for each hand. Volunteers of both sexes, aged 18-65 years with mild-moderate skin roughness and laxity at the level of hand dorsum are to be treated.

Primary endpoint of the study is the evaluation of performance and tolerance of Prohilo Body (3ml) treatment in the back of the hands (or dorsum of the hands).

Secondary endpoint is self-assessment questionnaire by both doctors and volunteers.

2. MATERIALS

- Prohilo Body® (IBSA Farmaceutici Italia S.r.l. - see Appendix 1)
- 22 G, 40mm, Magic needles
- Digital camera
- Dermal Torque Meter (Dia-Stron LTD)
- MoistureMeterD (Delfin Technologies, Kuopio - Finland)
- Primos compact portable (GFMesstechnik).

3. STUDY DEVICE

Prohilo® Body (IBSA Farmaceutici Italia S.r.l.) is a resorbable medical device 3.25 ml non-pyrogenic pre-filled syringe, containing 3 ml of 3.2% hyaluronic acid for intradermal use (48 mg H-HA + 48 mg L-HA) dissolved in 3 ml of saline buffered sodium chloride. – IBSA Farmaceutici Italia S.r.l. – ITALY. The principle component is cross-linked Hyaluronic Acid of non-animal origin, produced by bacterial fermentation (see Appendix 1).

On the basis of preceding trials with Prohilo® product, no reaction like injection site reaction, allergies and hypersensitivity reactions (see appendices 1) have been observed. This is due to the fact that this hyaluronic acid is not derived from animal tissue. Some side effects, like little bleeding and/or ecchymosis can happen shortly after injection.

DERMING S.r.l., Clinical Research and Bioengineering Institute [name]

[contact] - www.derming.com

Test code: E0122

4. DESIGN OF THE STUDY

Open, monocentric.

3 visits, 55 subjects.

T0: inclusion/exclusion criteria**, instrumental and clinical evaluation*, 1° treatment

T1 (after 1 month): instrumental and clinical evaluation, 2° treatment

[figure not shown]
T2 (3 months after T1; 4 months after T0): instrumental and clinical evaluation, NO treatment

Visit number	Study Activities	Treatment
1 T0	
Information and consent form provided. If participants agreeable, to sign consent form.
 
Photographic assessment: - Clinical photography
 
Clinical assessment
 
Instrumental assessment
 
First treatment of Profhilo® (refer to study protocol)
	
Prophilo Body 3 ml 1.5 ml per hand injected by a blunt tip microcannula (25G or 22G, preferably 22G), with fanning technique through a single entry point performing 5 passages and injecting 0,3 ml per passage.

2 T1 (1 month after T0)	
Photographic assessment: - Clinical photography
 
Clinical assessment
 
Instrumental assessment
 
Second treatment of Profhilo® (refer to study protocol)
 
Self-evaluation questionnaire
	
Prophilo Body 3 ml 1.5 ml per hand injected by a blunt tip microcannula (25G or 22G, preferably 22G), with fanning technique through a single entry point performing 5 passages and injecting 0,3 ml per passage.

3 T2 (4 months after T0)	
Photographic assessment: - Clinical photography
 
Clinical assessment
 
Instrumental assessment
 
NO treatment
 
Self-evaluation questionnaire
	No

DERMING S.r.l., Clinical Research and Bioengineering Institute [name]

[figure not shown]
[contact] - www.derming.com

Test code: E0122

4.1 INJECTION METHOD

Fanning technique with single entry point, 5 passages with cannula (25G or 22G, preferably 22G), 0,3 ml per passage, 1,5 ml for each hand.

5. RECRUITMENT OF THE VOLUNTEERS

5.1. Characteristics of the population

The study will be conducted on volunteers of both sexes, aged between 18 and 65 years, who meet the inclusion and exclusion criteria required by the study procedure.

5.2. Number of volunteers

In order to obtain at least 50 evaluable cases, 55 volunteers will be enrolled in the trial

5.3 Inclusion criteria

Will be included in the study volunteers with the following characteristics:

- female and male sex, not necessarily 1:1 ratio;

DERMING S.r.l., Clinical Research and Bioengineering Institute [name]

[contact] - www.derming.com

Test code: E0122

- age 18-65 years;
- asking for hands restoration;
- available and able to return to the study site for the post-procedural follow-up examinations;
- accepting to not change their habits regarding food, physical activity, cosmetic and cleansing products for the hands;
- accepting not to expose their hands to strong UV irradiation (UV session, or sun bathes) during the entire duration of the study, without appropriate sun protection;

5.4 Exclusion criteria

- Pregnancy;
- lactation;
- smokers;
- alcohol or drug abusers;
- subjects not in menopause who do not use adequate contraceptive precautions in order to avoid pregnancies during the study;
- Body Mass Index (BMI) variation (± 1) during the study period;
- performing non-surgical skin aesthetic procedures for hands in the 6 months prior to the study start;
- aesthetic surgical procedure for the hands in the past;
- change in the normal habits regarding food, physical activity, cosmetic products and cleansing for the hands during the month preceding the test;
- sensitivity to the test product or its ingredients (to be assessed by the investigator during the baseline visit);
- subjects whose insufficient adhesion to the study protocol is foreseeable;
- participation in a similar study currently or during the previous 6 months.)
- presence of cutaneous disease on the tested area, as lesions, scars, malformations;
 - clinical and significant skin condition on the test area (e.g. active eczema, psoriasis, scleroderma, local infections).

5.4.1 Exclusion criteria due to systemic disease

- Diabetes;
- endocrine disease;
- hepatic disorder;
- renal disorder;
- cardiac disorder;
- pulmonary disease;
- cancer;
- neurological or psychological disease;
- inflammatory/immunosuppressive disease;
- drug allergy

5.4.2. Exclusion criteria due to ongoing pharmacological treatment

- Anticoagulants and antiplatelet drugs, anti-histaminic, topical and systemic corticosteroids, narcotic, antidepressant, immunosuppressive drugs (with the exception of contraceptive or hormonal treatment starting more than 1 year ago);
- using of drugs able to influence the test results in the investigator opinion.

The use of other drugs, not mentioned above, can be authorized by the Investigator. The trade name, the dosage, the start and stop date of the therapy will be reported on concomitant medication form.

DERMING S.r.l., Clinical Research and Bioengineering Institute [name]

[contact] - www.derming.com

Test code: E0122

5.4.3. Restrictions

The volunteers accept to respect the rules fixed in the list of recruitment criteria and not to deviate from their normal life habits; particular attention should be paid to the cosmetic products and detergents for the hands, which must remain the same during the entire study period. During the entire period of treatment, the exposure to strong UV irradiation (UV session, or sun bathes) without appropriate sun protection, will be avoided. Moreover the use of NSAID drugs is not admitted in the 5 days preceding the two injective procedure.

6. CASE RECORD FORM (CRF)

The investigator will use an electronic CRF (eCRF) specially “ad hoc” engineered for each study by a trained and specialized DERMING technician. In the eCRF all information about subjects (personal data, subject’s history, inclusion/exclusion criteria, clinical evaluations, instrumental data etc.) will be recorded directly on a tablet (interactive form). The tabulation of the collected data is direct and totally automatic (not manual), assuring an higher level of quality and security. Every step of the eCRF creation and filling processes are performed in accordance to DERMING internal quality procedure assuring the validation of data and the prevention of data loss.

7. SAMPLE ACCEPTANCE, IDENTIFICATION AND APPLICATION

IBSA will supply directly the study center and samples will be stored as indicated by the Instruction for Use. Samples are handled by DERMING in accordance with the methods described in the company operating procedures (SOP).

The products to be tested are recorded, with a reference number, in the Human Studies Record Book together with additional information such as the arrival date, the test requested, Company’s name, the product code, the order number and any other information reported on the container.

During the twelve months following the issue date of the report, a counter-sample will be kept in the same conditions as those described above.

8. TREATMENT EVALUATION

8.1. Inclusion visit

Each volunteer is submitted to a careful clinical examination in order to check the selection criteria.

8.2. Efficacy evaluation

The assessment of the aesthetic result will be established through the use of qualitative (clinical evaluations) and quantitative assessments (instrumental measurements) and supported by photographic documentation.

All clinical and instrumental evaluations will be carried out mono-laterally on hands, right or left side according to a subjects’ randomization list defined by the investigator before the subjects’ inclusion. The evaluation side assigned at each enrolled subject will be recorded in the eCRF.

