8.2.1. Clinical evaluations

Clinical assessment of hand dorsum (according to a reference photographic scale) roughness and laxity will be performed at each study time according to a visual score from 1 (no roughness and flaccidity) to 5 (very severe roughness and flaccidity).

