8.2.2. Photographic documentation

2D pictures of the dorsum of both hands for all included volunteers will be taken. In order to assure comparable images, the pictures will be taken with standardised methods, concerning especially:

- magnification factor

DERMING S.r.l., Clinical Research and Bioengineering Institute [name]

[contact] - www.derming.com

Test code: E0122

- intensity of illumination source (photographic lamps)

- angle of incidence and inclination of illumination

More-over the subject during the photo execution must keep still, with relaxed body muscles.

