12.3. Clinical data

The statistical analysis of clinical data is carried out with not parametric test.

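### The 1–5 visual score is taken on one hand although both hands are treated and photographed; grading both would buy some precision at little cost

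*Combined protocol and SAP*

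**What the plan says.** - **Treatment.** Section 4.1 specifies "1,5 ml for each hand", and the visit table in section 4 repeats this for T0 and T1. Both hands are treated, in the same way and at the same visits.
- **Photographs.** Section 8.2.2: "2D pictures of the dorsum of both hands for all included volunteers will be taken". Sections 4 and 10 schedule photography at T0, T1 and T2.
- **Scoring.** Section 8.2: "All clinical and instrumental evaluations will be carried out mono-laterally on hands". The side comes from a randomisation list that the investigator draws up before anyone is included, and "The evaluation side assigned at each enrolled subject will be recorded in the eCRF".
- **Clinical score.** Section 8.2.1 describes a visual grade from 1 to 5, made against a photographic scale at every study time. Section 2 lists no measuring device for it.
- **Sample size.** Section 5.2: "In order to obtain at least 50 evaluable cases, 55 volunteers will be enrolled in the trial". No effect size, standard deviation or power accompanies these numbers.
- **Analysis.** Section 12.3: "The statistical analysis of clinical data is carried out with not parametric test". Section 12.5 compares each study time with T0.

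The documents give no reason for scoring one hand.

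**The concern.** For the instruments a one-hand rule is easy to understand. Torsiometry needs an adhesive probe, profilometry needs a pinched fold of skin and a 3D image, and the dielectric measurement uses two probes. The visual grade has none of these burdens, yet the same sentence in section 8.2 restricts it too. At each visit the second treated hand is present and photographed, but it adds nothing to the investigator's score.

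What is at stake is the precision of the mean change in the clinical score. A lesser point is resolution. Section 1 describes subjects with mild to moderate roughness and laxity, so whole-grade changes on a five-point scale are likely to produce many ties. A mean of two hands can move in half grades.

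**Working it through.** **The plan's own figure.** There is no power calculation to reproduce. The pair 55 enrolled and 50 evaluable implies an allowance of 1 − 50/55 = 9.1% for loss. I use n = 50 subjects below.

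**Inputs.**
- Hands treated: 2 (section 4.1). Hands photographed: 2 (section 8.2.2). Hands scored: 1 (section 8.2).
- Evaluable subjects: 50 (section 5.2).
- Between-hand correlation of the change from T0 (rho): not in the documents. Assumed, from 0.3 to 0.95.
- Equal variance of change in the two hands: assumed.

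**Formula.** Let each hand's change have variance V. The mean of the two hands has variance (V + V + 2·rho·V)/4 = V(1+rho)/2. Relative to one hand:
- the variance ratio is (1+rho)/2, so the reduction is (1−rho)/2;
- the equivalent number of one-hand subjects is 50 ÷ [(1+rho)/2];
- the standard error falls by 1 − √[(1+rho)/2].

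| Assumed rho | Variance ratio | Variance falls by | Equivalent one-hand subjects | Standard error falls by |
|---|---|---|---|---|
| 0.3 | 0.650 | 35% | 50/0.650 = 76.9 | 19.4% |
| 0.5 | 0.750 | 25% | 50/0.750 = 66.7 | 13.4% |
| 0.8 | 0.900 | 10% | 50/0.900 = 55.6 | 5.1% |
| 0.9 | 0.950 | 5% | 50/0.950 = 52.6 | 2.5% |
| 0.95 | 0.975 | 2.5% | 50/0.975 = 51.3 | 1.3% |

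Simulating 400,000 bivariate normal pairs gives reductions of 34.8% at rho 0.3 and 9.8% at rho 0.8, which agrees with the formula.

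**Illustration as a detectable change.** The plan states neither an efficacy alpha nor a power, so I assume two-sided 5% and 80% with a normal approximation. With one hand, the detectable mean change is (1.960 + 0.842)/√50 = 0.396 standard deviations of the one-hand change. With two hands averaged it is 0.396 × √0.650 = 0.319 at rho 0.3, 0.396 × √0.900 = 0.376 at rho 0.8, and 0.386 at rho 0.9.

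**Limits.** The formula describes a mean. For a coarse ordinal score under a non-parametric test that the plan does not name, the equivalent sample sizes are only a guide.

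**The case against.** The strongest objection is that one-hand scoring is a legitimate design. The side is fixed by a list before inclusion, so nobody can pick the better hand. Each subject gives one independent value, taken on the same hand as the instruments. All of this stands: the choice costs efficiency and is not an error.

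The gain may also be small. Both hands belong to one person, receive the same product and technique, and would be graded by someone who knows the treatment. Shared biology and shared expectation push rho up, and at 0.9 or above the variance falls by 5% or less. Grading error that is independent between hands pulls rho down. The documents do not show which dominates, so the upper end of the range has to be taken seriously. A modest gain in precision also does nothing about the absence of a control group.

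A reader might infer more than the documents support:
- *That the clinical result is biased.* It is not, because the side is set before inclusion.
- *That the trial is underpowered.* No power target, effect size or success threshold is stated, so none can be shown to be missed.
- *That half of the treated area is ignored.* This is true only of the investigator's and instrumental evaluations. The volunteer questionnaire (section 8.3) concerns the treated areas, and tolerance recording (section 9.1) is not limited to one side.
- *That a difference between hands would go unseen.* Both hands are photographed under standardised conditions, and the recorded side allows left and right to be compared between subjects. No objective concerns such a difference.

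**Conclusion.** The point holds as a cheap improvement of minor importance. Applying the one-hand rule to the visual score forgoes precision. Under equal variances, averaging two hands helps at any rho below 1 and does no harm at rho = 1. The reduction in the variance of the mean change runs from 35% at an assumed rho of 0.3, through 10% at 0.8, to 2.5% at 0.95. That is equivalent to between about 77 and 51 one-hand subjects in place of 50. The size rests entirely on rho, which the documents do not give, and it is approximate for the planned non-parametric analysis. No stated conclusion of the trial depends on it.

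**What to change.** - In section 8.2, limit the one-hand rule to the instrumental measurements, and keep the randomisation list for them.
- In section 8.2.1, have the 1–5 score graded on both hands at T0, T1 and T2.
- In section 12.3, define the analysis variable as the within-subject mean of the two hands. This gives one value per subject, so the sample size remains the number of subjects. The two hands must not be counted as independent observations.
- Keep the score of the randomised hand as a sensitivity analysis. This preserves the link to the instrumental data on the same hand.

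The cost is one more visual grade against the photographic scale and one more eCRF field at each of the three visits. No extra instrument measurement or visit is needed. The documents do not say how long a grade takes.

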8.2.1. Clinical evaluations

Clinical assessment of hand dorsum (according to a reference photographic scale) roughness and laxity will be performed at each study time according to a visual score from 1 (no roughness and flaccidity) to 5 (very severe roughness and flaccidity).

8.2.2. Photographic documentation

2D pictures of the dorsum of both hands for all included volunteers will be taken. In order to assure comparable images, the pictures will be taken with standardised methods, concerning especially:

- magnification factor

DERMING S.r.l., Clinical Research and Bioengineering Institute [name]

[contact] - www.derming.com

Test code: E0122

- intensity of illumination source (photographic lamps)

- angle of incidence and inclination of illumination

More-over the subject during the photo execution must keep still, with relaxed body muscles.

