15. APPENDICES

- 1) Product information and complications of injectable fillers
- 2) Adverse event and concomitant medication forms
- 3) Informed consent form and subjects' enrolment form
- 4) Certificate of subjects information
- 5) Volunteers' self assessment questionnaire
- 6) Consent form to the personal data processing (European General Data Protection Regulation - GDPR 2016/679)
- 7) Helsinki declaration
- 8) Inner arm reference photographic scale
- 9) "Torque on" and "torque off" curves.

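### The 1-5 clinical score is given at each visit with no masking described; the photographs already taken at every visit could be graded with the visit hidden, as a supporting analysis.

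*Combined protocol and SAP*

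**What the plan says.** Section 4 describes the design as "Open, monocentric", with "3 visits, 55 subjects". All subjects are treated and there is no control arm.

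Section 8.2.1 defines the clinical score: "Clinical assessment of hand dorsum (according to a reference photographic scale) roughness and laxity will be performed at each study time", on a scale from 1 (best) to 5 (worst). Sections 10.1 and 10.2 place this assessment at the same visits as the two injections; T2 has no treatment. Section 12.5 expresses the result against T0, and section 12.3 analyses clinical data with an unnamed nonparametric test.

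On photographs, section 8.2.2 says "2D pictures of the dorsum of both hands for all included volunteers will be taken", with magnification, light intensity and the angle of the lighting standardised so that images are comparable. The section 4 table and sections 10.1 to 10.3 list photography at T0, T1 and T2. Section 8.2 gives the photographs a supporting role only, and no grading of them is planned.

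No section provides for a masked or independent assessor. The randomization list in section 8.2 decides which hand is evaluated; it masks nothing.

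The live score is graded "according to a reference photographic scale", but the only such scale in section 15 is Appendix 8, "Inner arm reference photographic scale".

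**The concern.** A five-step visual grade is a judgement. A grader who knows that the hand has been treated may lean towards a better grade, without intending to. In a controlled trial with masked assessors, such a lean would fall on both arms and largely cancel. Here there is no second arm, so it becomes part of the estimated effect, and nothing in the clinical data would reveal it.

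Performance is part of the primary endpoint in section 1, and section 8.2 makes the clinical score one of the measures that establish the aesthetic result. The plan already collects images that would allow a check on this bias, but does not use them for it.

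**Working it through.** **What the plan's own figures give.** Section 5.2 states: "In order to obtain at least 50 evaluable cases, 55 volunteers will be enrolled in the trial". The implied loss is (55 − 50)/55 = 9.1%. No alpha, power, effect size or SD is stated, so there is no power calculation to reproduce. The 50 evaluable subjects are used below.

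**Does the grader know the visit?** The score "will be performed at each study time according to a visual score from 1" onwards, so grading happens at the visit. The study is open, and no masking step appears in sections 4, 8 or 10. The documents neither name the grader nor say what the grader knows. Knowledge of the visit is therefore an inference, though a strong one.

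**How much could it matter?** Inputs:

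- n = 50 (section 5.2).
- Two-sided 5% level (assumed).
- SD of the change: 0.5, 0.7 or 0.9 points (assumed).
- True change: zero.
- Expectation effect: a fraction q of hands is scored one point better at follow-up (assumed). The mean then shifts by q × 1 point in the direction of improvement.

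Under a paired t-test with 49 degrees of freedom, the critical value is 2.010 and the non-centrality is δ = (q / SD) × √50. The chance of a significant result is P(|T| > 2.010), where T is non-central t with parameter δ.

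| q | SD | δ | Chance of p < 0.05 |
|---|---|---|---|
| 0.10 | 0.5 | 0.10/0.5 × 7.071 = 1.41 | 28.4% |
| 0.10 | 0.7 | 1.01 | 16.8% |
| 0.10 | 0.9 | 0.79 | 12.0% |
| 0.25 | 0.5 | 0.25/0.5 × 7.071 = 3.54 | 93.4% |
| 0.25 | 0.7 | 2.53 | 69.7% |
| 0.25 | 0.9 | 1.96 | 48.6% |

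With q = 0 the figure is 5%.

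**Check with a nonparametric test.** Section 12.3 plans one, so whole-number changes of −1, 0 and +1 were simulated with probabilities 0.2, 0.6 and 0.2, and tested with the Wilcoxon signed-rank test at n = 50. Significant results came to about 5% with no bias, 17% at 1 hand in 10 and 63% at 1 hand in 4. The message does not depend on the t approximation.

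**Workload of a masked reading.** One evaluated hand per subject: 55 × 3 = 165 images, or 50 × 3 = 150 if only completers are read. At an assumed 1 minute each, 165 minutes is 2.75 hours.

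**The case against.** Several points on the other side are sound.

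- *The clinical score does not stand alone.* A reader might infer that it is the only clinician-rated measure and that masking is the only safeguard. The documents support neither. Section 1 mentions a questionnaire completed by doctors as well as volunteers, although section 8.3 details only the volunteers' form. Section 8.2.3 adds dielectric constant, profilometry and torsiometry, which are far less open to expectation, though not free of operator effects. These are separate evidence; they do not correct the clinical score, which section 12.3 analyses on its own.
- *A photograph is not the hand.* A reader might conclude that a masked score should replace the live one. Laxity shows less well in 2D, and the score combines roughness with laxity, so replacement would trade a bias for a loss of validity of unknown size. Section 8.2.2 lists the angle of the lighting but not camera angle or hand posture, although its list may not be exhaustive. This stands, and limits the masked reading to a supporting role.
- *The same assessor may recognise hands.* This stands in part. Recognising a hand does not reveal which visit an image comes from, but a reader who neither treated nor graded that subject is better. The documents do not describe staffing, so whether one is available is a feasibility judgement.
- *The scale is not settled.* An inner arm scale cannot be assumed to serve for the hand dorsum. This stands, and has to be resolved before any photograph is graded.
- *The design is declared as uncontrolled.* True. Masked reading would not remove regression to the mean or seasonal change.

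**Conclusion.** The point holds as a worthwhile improvement to the plan. A subjective score, given at the visit in an open single-arm study and compared with T0, has no described protection against expectation in grading, while comparable photographs from all three visits go ungraded.

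The size is illustrative. With 50 subjects, no true effect and a two-sided 5% level, the chance of a significant clinical result rises from 5% to between 12% and 28% if 1 hand in 10 is favoured by a point, and to between 49% and 93% if 1 in 4 is, for an SD of change from 0.9 to 0.5. Neither the SD nor the rates of favoured scoring come from the documents. A reader might take these figures as a forecast, or as evidence that the live scores will be biased; they are neither. They show that a small lean would be enough.

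**What to change.** Add to sections 8.2.1 and 12.3:

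1. After the last T2 visit, existing site staff grade the photographs of each subject's evaluated hand on the 1-5 scale. The reader is preferably someone who did not treat or grade that subject; otherwise it is the same assessor.
2. Dates are removed, and images are coded and shuffled across subjects and visits. Images are checked beforehand for visible injection marks that would reveal the visit.
3. The change from T0 in the masked score is reported beside the live score as a prespecified supporting analysis. The live score is kept. If the two disagree, the clinical conclusion is tempered accordingly.

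Before any grading, reconcile section 8.2.1 (hand dorsum) with Appendix 8 as listed in section 15 (inner arm), so that live and photographic grades use the same stated scale.

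The cost is about 165 images, roughly 3 hours of grading at the assumed 1 minute each, plus time for coding and removing dates. No visit, procedure or treatment changes. The report should say that masked reading addresses expectation in grading only.
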